6. CONCOMITANT MEDICATIONS/TREATMENT

The patient will be queried regarding concomitant use of medications at all study visits. All concomitant medication use (both prescription and over-the-counter, including herbal medications and nutritional supplements) will be reported during the study, and recorded in the patient's study file.

Patient will be instructed to avoid any oral supplements containing omega-3 fatty acid supplements during this protocol.

The patient may receive other lipids to meet essential fatty acid (EFA) and/or additional calorie needs.

7. COMPLIANCE

Treatment compliance can be assessed using drug accountability records. The home healthcare nurse will collect any used/unused bottles at each visit and maintain a patient accountability record of all study medication that is distributed, administered, and collected for destruction.

8. INVESTIGATIONAL MATERIALS AND MANAGEMENT

8.1. Investigational Product

8.1.1. General Investigational Product Information

Bottles containing 50 mL or 100 mL of 10% Omegaven will be purchased from International Pharmacy of Hamburg, Germany. Omegaven is manufactured by Fresenius Kabi AG, Bad Homburg v.d.h, Germany. Omegaven is formulated as an emulsion from fish oils.

8.1.2. Dosing

Patients will be treated with Omegaven on day 1 at a dose of 0.1 g/kg body weight (1 ml/kg). On day 2 or 3, it will be increased to 0.2 g/kg body weight (2 ml/kg). For patients > 120% ideal body weight, adjusted body weight will be used for dosing. The infusion rate will not exceed 0.5 ml Omegaven/kg body weight/hr = 0.05 g fish oil/kg body weight/hr.

Omegaven will be co-infused via a y-site. Containers will be changed every 12 hours. Omegaven will be given through a 1.2 micron inline filter.

Omegaven will be given for:

- 4 weeks, or
- Until serum bilirubin is < 2 mg/dL, or
- Until normalization of liver function tests.

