Patients who have been receiving treatment at CTCA and have been receiving outpatient PN and develop PNinduced hepatic injury, or will be starting home PN and have existing hepatic dysfunction.

Patients will receive their initial infusion of PN containing Omegaven at a CTCA location to observe for adverse reactions. Omegaven will be given on Day 1 at a dose of 0.1 g/kg body weight (1 mL/kg). On Day 2 or 3, it will be increased to 0.2 g/kg body weight (2 mL/kg). The infusion rate will not exceed 0.5mL Omegaven/kg body weight/hr (corresponding to 0.05g fish oil/kg/hr).

After tolerance is established, patients will have the option to receive treatment at home through Coram for 4 weeks or until hepatic dysfunction is reversed (established normalization of liver function tests/serum bilirubin < 2).

INCLUSION CRITERIA:

A patient must meet the following criteria to participate in this study:

- I.1 Male or Female; ages 18 to 80
- **I.2** Receiving treatment at CTCA
- **I.3** Receiving PN (either in the infusion center or at home)
- I.4 Have existing hepatic dysfunction defined as Elevation of >3x the normal level of one or more of the following: Alkaline Phosphatase (ALP), Aspartate Aminotransferase (AST), or Alanine Aminotransferase (ALT) and/or Bilirubin > 2 mg/dl in the absence of biliary obstruction.
- **1.5** Able to provide informed written consent (patient or legally acceptable representative)

EXCLUSION CRITERIA:

Patients will be excluded from participating in the study for the following reasons:

- **E.1** Hypertriglyceridemia (fasting triglycerides [TG] > 400)
- E.2 Allergy to fish or egg protein
- **E.3** Currently on therapeutic doses of Coumadin, heparin, or low molecular weight heparin.
- **E.4** Hemodynamically unstable
- **E.5** Bilirubin > 5 mg/dL
- **E.6** Documented progression of liver metastases
- **E.7** Unstable diabetes with known diabetic ketoacidosis within 7 days of screening
- E.8 Recent cardiac infarction taking plavix
- **E.9** Severe hemorrhagic disorders

E.10 Embolism

- E.11 Sepsis
- **E.12** Undefined coma status
- **E.13** Renal insufficiency with calculated creatinine clearance < 30 mL/min.
- **E.14** Pregnancy or lactation

TREATMENT:

Treatment with Omegaven will be given on study Day 1 at a dose of 0.1 g/kg body weight (1 mL/kg). On Day 2 or 3, it will be increased to 0.2 g/kg body weight (2 mL/kg). The infusion rate will not exceed 0.5mL Omegaven/kg body weight/hr (corresponding to 0.05g fish oil/kg/hr).

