Omegaven will be co-infused via y-site. Containers will be changed every 12 hours. Omegaven will be given through a 1.2 micron inline filter.

Omegaven will be given daily for:

- Up to 4 weeks, or
- Until normalization of alkaline phosphatase, AST, & ALT

The patient may receive other lipids to meet essential fatty acid (EFA) and/or additional calorie needs.

EFFICACY OUTCOME VARIABLES:

- Maximum conjugated bilirubin
- Time to resolution of bilirubin or death
- Average improvement in bilirubin, alkaline phosphatase, AST, & ALT

SAFETY OUTCOME VARIABLES:

- Summary of laboratory results
- Summary of AEs for each patient

			Table of Contents	
1.	LIST OF ABBREVIATIONS AND DEFINITIONS OF TERMS			6
2.		INTRO	DUCTION	7
	2.1.	Backgrou	nd	7
	2.2.	Risk Cate	gory	8
	2.3.	Rationale)	8
	2.4.	Statemer	nt	8
3.		OBJEC	ΓΙVES	8
4.		INVEST	IGATONAL PLAN	9
	4.1.	Study De	sign	9
	4.2.	Study Pro	ocedures by Visit	10
		4.2.1. S	creening Visit	10
		4.2.2. C	Day 1 Visit	10
		4.2.3. E	Day 2/Day 3 Visit	10
		4.2.4. C	Day 5 Visit	10
		4.2.5. V	Neekly Visits During Home Use of Omegaven (up to 4 weeks of treatment)	11
		4.2.6. F	inal Study Visit/Early Withdrawal Visit	11
	4.3.	Description	on of Study-Specific Procedures	11
		4.3.1. C	Diagnostic Tests	11
5.		SELECT	ION AND WITHDRAWAL OF PATIENTS	12
	5.1.	Patient Ir	clusion Criteria	12
	5.2.	Patient E	xclusion Criteria	12
	5.3.	Patient W	/ithdrawal Criteria	12
6.		CONCO	OMITANT MEDICATIONS/TREATMENT	13
7.		COMPI	LIANCE	13
8.		INVEST	IGATIONAL MATERIALS AND MANAGEMENT	13
	8.1.	Investiga	tional Product	13
		8.1.1. 0	General Investigational Product Information	13
		8.1.2. C	Dosing	14
		8.1.3. C	Dispensation	14
		8.1.4. 5	torage and Handling	14
		8.1.5. A	Accountability	14
		8.1.6. C	Dose Adjustments	14
9.		ASSESS	MENT OF EFFICACY AND SAFETY	14
	9.1.	Outcome	Variables	14
	9.2.	Adverse I	Event (AE) Recording/Reporting	14
	9.3.	Serious A	dverse Event (SAE) Recording/Reporting	16
	9.4.	IND Safet	y Reporting	16
		9.4.1. V	Vritten IND Safety Report	17
		9.4.2. T	elephone or Fax IND Safety Reports	17
	9.5.	IRB Safet	y Reporting	17
10.		DATA I	MANAGEMENT	17
	10.1.	Data Mar	nagement	17
	10.2.	Sample S	ize Determination	17
	10.3.	Dispositio	on and Baseline Assessment	17
	10.4.	Outcome	s Analysis	17
	10.5.	Data Mor	nitoring Committee	18
	10.6.	Study Ter	mination	18

	10.7.	Study Medication Administration	. 18
	10.8.	Concomitant Medications	. 18
11.		STUDY ADMINISTRATION	. 18
	11.1.	Adherence to the Protocol	. 18
	11.2.	Amending the Protocol	. 19

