2. INTRODUCTION

2.1. Background

Parenteral nutrition (PN), when required for long-term nutrition support, may lead to hepatic dysfunction (ADA pocket guide to PN). PN can be the cause of hyperbilirubinemia and elevated liver function tests. Patients at increased risk of developing hepatic dysfunction from PN are those with primary gastrointestinal disorder, pre-existing liver disease, malnutrition, or sepsis (ref). The cause of this dysfunction may be related to the provision of excess calories, excess individual macronutrients, and deficiencies of choline, L-carnitine, and/or glutamine. This dysfunction can progress to liver failure in patients requiring long-term PN.

There are recommendations to try to prevent PN induced hepatic dysfunction. They include but are not limited to avoiding excess calorie, carbohydrate, and/or lipid infusion; limiting infusion time; some oral or enteral nutrients if possible; and possibly adding choline, L-carnitine, and/or glutamine to the PN. Despite following these recommendations, patients may still develop PN induced hepatic dysfunction. This may result in the need to discontinue PN.

Patients with advanced cancer requiring PN for long-term nutrition support may be at increased risk for developing this condition due to gastrointestinal failure, liver metastases, and malnutrition. If these individuals begin to experience elevation of bilirubin and/or liver function tests, the calories from macronutrients may have to be reduced, resulting in underfeeding in those that may already be malnourished. If after reducing calories from macronutrients and adding L-carnitine to the PN, liver function does not improve, the PN may have to be held or discontinued. This results in severe under nutrition or in some cases no source of nutrition.

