4. INVESTIGATIONAL PLAN

4.1. Study Design

This compassionate use study will include patients with advanced cancer requiring PN for long-term nutrition support who have developed PN-induced hepatic injury or who have existing hepatic dysfunction. Therapy with Omegaven will be provided at an initial dose of 0.1 g/kg body weight (1ml/kg) and increased to 0.2 g/kg body weight (2ml/kg) on day 2 or 3 of treatment. For patients > 120% ideal body weight, adjusted body weight will be used. The infusion rate will not exceed 0.5mL Omegaven/kg body weight/hr (corresponding to 0.05g fish oil/kg/hr). Omegaven will be co-administered via a y-site infusion, with containers being changed every 12 hours. The patient may receive other lipids to meet Essential Fatty Acid (EFA) and/or additional calorie needs. Patients will receive the initial infusion of PN containing Omegaven at Midwestern Regional Medical Center (MRMC) in the infusion center to observe for adverse reactions. If an adverse reaction is observed, IV steroids & benadryl will be administered & Omegaven will be discontinued. Patients will continue to receive infusions at CTCA for the first 2 to 3 days of dosing. After tolerance is established, patients will receive treatment at home with Coram. All study patients will have a Screening Visit; Day 1, Day 2 and Day 3 visits; and weekly visits for one month (see Table 2).

					Weekly	Final Study Visit/
Visit:	Screening	Day 1	Day 2	Day 3	Visits	Early Withdrawal
Informed Consent Form	Х					
Inclusion/Exclusion Criteria	Х					
Physical Exam	Х					Х
Vital Signs	Х	Х	Х	х	Х	Х
Medical History	Х					
Blood hematology/chemistry	Х	Х	Х	Х	Х	Х
Triglyceride level monitoring ¹		Х	Х	Х	Х	
Dispense study medication		Х	Х	Х	Х	
Infusion given at MRMC ²		Х	Х			
Infusion given at MRMC or at the patient's home				х	х	
Adverse Events (AEs)		Х	Х	Х	х	Х
Concomitant medications		Х	Х	Х	Х	Х
Education on home PN &		v				
Omegaven		^				
Assess patient compliance				Х	Х	
Clinical supplies accounted for & destroyed						x

Table 2: Study Schedule

¹ Triglyceride level monitoring will occur daily from the time the patient begins Omegaven dosing until Omegaven dosing is complete.

² Infusions will be given at MRMC for 2-5 days, after which the infusions can be moved to the patient's home.

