4.2.3. Day 2 Visit

The Day 2/Day 3 Visit will occur at CTCA. At this visit, the following will occur for all patients:

- Vital signs will be taken.
- Blood will be drawn for hematology and chemistry lab panels (see Section 4.3.1).
- Omegaven dosing will occur via continuous infusion at CTCA. The infusion rate will not exceed 0.5mL Omegaven/kg body weight/hr (corresponding to 0.05g fish oil/kg/hr).
- The Omegaven dose will be increased to 0.2 g/kg body weight (2 ml/kg).
- AEs and Concomitant Medications since the previous visit will be recorded.

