5. SELECTION AND WITHDRAWAL OF PATIENTS

5.1. Patient Inclusion Criteria

A patient must meet the following criteria to be included in this study:

- I.1 Male of Female; ages 18 to 80
- I.2 Receiving treatment at CTCA
- I.3 Receiving PN (either in the infusion center or at home)
- I.4 Have existing hepatic dysfunction defined as Elevation of >3x the normal level of one or more of the following: Alkaline Phosphatase (ALP), Aspartate Aminotransferase (AST), or Alanine Aminotransferase (ALT) and/or Bilirubin > 2 mg/dl in the absence of biliary obstruction.
- 1.5 Able to provide informed written consent (patient or legally acceptable representative)

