5.3. Patient Withdrawal Criteria

Patients may be terminated from the study for the following events and reasons:

- W.1 The patient chooses to withdraw for any reason
- W.2 The Investigator chooses to terminate the patient from the study. Reasons could include:

- a. Occurrence of AEs related to the use of Omegaven; adverse reaction to Omegaven
- b. Patient non-compliance
- c. Patient discovered after enrollment not to have met the protocol entrance criteria
- W.3 Therapy goals are reached: patient able to meet and sustain nutrient needs by oral nutrition
- W.4 Patient lost to follow-up
- W.5 The principal-investigator terminates the study
- W.6 If bilirubin elevates to > 5 mg/dl due to obstruction
- W.7 Requires open surgical procedure
- W.8 Documented progression of liver metastases contributing to worsening of hepatic dysfunction.

If a patient does not return for a scheduled visit every effort should be made to contact the patient. In any circumstance, every effort should be made to document patient outcome, if possible. Patients will only be considered lost to follow-up if study personnel are unable to communicate with the patient or the patient's legally acceptable representative by three telephone attempts and certified letter. Reasons for withdrawal will be specified in the patient's study file, and will include date of discontinuation of investigational product and date of study withdrawal.

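### The Protocol gives incompatible rules for stopping Omegaven when bilirubin is below 2 mg/dL but liver enzymes are still raised, and a patient admitted on enzymes alone can meet the bilirubin limb at entry

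*Protocol*

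**What the plan says.** The end of treatment is described in four places in the Protocol.

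- **Sections 4.2.5 and 8.1.2** agree with each other. Treatment ends at 4 weeks, or at the bilirubin limb, "Until serum bilirubin is < 2 mg/dL, or" when liver function tests are normal. Each limb is sufficient alone.
- **Synopsis, Treatment:** daily dosing for at most 4 weeks, or "Until normalization of alkaline phosphatase, AST, & ALT". Bilirubin is not mentioned.
- **Synopsis, Study Design:** 4 weeks, or "until hepatic dysfunction is reversed (established normalization of liver function tests/serum bilirubin < 2". The meaning of the slash is not given.

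Entry is set by criterion I.4 in section 5.1: a value above three times normal in "one or more of the following: Alkaline Phosphatase (ALP), Aspartate Aminotransferase (AST), or Alanine Aminotransferase (ALT) and/or Bilirubin > 2 mg/dl". Either route is enough, so a patient may enter on an enzyme with bilirubin below 2, or on bilirubin with normal enzymes.

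Section 5.3 does not settle the matter. Criterion W.3 reads "Therapy goals are reached: patient able to meet and sustain nutrient needs by oral nutrition" and names no liver value.

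**The concern.** The end of dosing is a treatment instruction that the protocol itself has to fix; an analysis plan cannot repair it. Here the body and the synopsis give opposite instructions for a laboratory pattern that can plausibly arise during follow-up: bilirubin settled, enzymes not.

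In addition, a response criterion should describe recovery from what was wrong at entry. For an enzyme-only patient with bilirubin below 2, the body's bilirubin limb is true before the first dose and so carries no information about response. For a bilirubin-only patient with normal enzymes, the same holds of the synopsis Treatment limb.

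Two things are at stake. Treatment could end while the qualifying injury persists, even though weeks remain under the cap. And the summaries become harder to interpret. Section 10.4 reports the incidence of resolution of hepatic injury and possibly the time to it, and section 10.7 requires deviations from planned dosing to be summarized. With two rules in force, the same stop date is compliant under one and a deviation under the other.

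**Working it through.** There is no stated figure to reproduce, so the check is a side-by-side reading followed by two small calculations.

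**1. The rules by laboratory state.** *Enzymes* means ALP, AST and ALT.

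| Bilirubin | Enzymes | 4.2.5 and 8.1.2 | Synopsis Treatment | Synopsis Study Design, slash = or | Slash = and |
|---|---|---|---|---|---|
| < 2 | all normal | stop | stop | stop | stop |
| < 2 | at least one raised (state A) | **stop** | **continue** | stop | continue |
| not < 2 | all normal (state B) | depends on what liver function tests include | stop | same as 4.2.5 and 8.1.2 | continue |
| not < 2 | at least one raised | continue | continue | continue | continue |

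State A is a firm conflict, whatever the phrase liver function tests covers. Reading the slash as *or* puts Study Design in conflict with the Treatment list; reading it as *and* puts it in conflict with the body sections. State B turns on definitions. Section 2.1 treats the terms as separate ("elevation of bilirubin and/or liver function tests"), whereas section 4.3.1 places direct and total bilirubin in the liver panel.

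**2. A charitable reading.** Suppose each limb applies only to an abnormality the patient actually has. Take a patient who enters with both bilirubin above 2 and ALP above three times normal, and whose bilirubin then falls below 2 while ALP stays raised. Section 8.1.2 still stops and the Treatment list still continues.

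**3. Counting patterns.** Give each of the three enzymes three levels (normal, 1 to 3 times, above 3 times) and bilirubin two levels (below or above 2, setting aside exactly 2). Take liver function tests to mean the enzymes.

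- All patterns: 3 × 3 × 3 × 2 = 54.
- Not qualifying under I.4 (no enzyme above 3 times, bilirubin below 2): 2 × 2 × 2 = 8, so 54 − 8 = 46 qualify.
- Already meeting the body rule at entry: 27 − 8 = 19 enzyme-only patterns with bilirubin below 2, plus 1 bilirubin-only pattern with normal enzymes, giving 20 of 46. If liver function tests include bilirubin, 19 of 46.
- Already meeting the Treatment list at entry: 1 of 46 (bilirubin-only, enzymes normal).
- Body rule and Treatment list disagree on 27 − 1 = 26 of 54 patterns, all in state A.

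These are counts of logical patterns, not expected proportions of patients.

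**4. Dose illustration.** Assume one dose a day for 28 days, 0.1 g/kg on Day 1, 0.2 g/kg from Day 2, no dose reduction, and no dose on the day the stop is triggered. After n doses the total is 0.1 + (n − 1) × 0.2 g/kg.

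- Full course: 0.1 + 27 × 0.2 = 5.5 g/kg.
- Weekly visit 1 (7 doses): 1.3 g/kg, 1.3/5.5 = 24%.
- Weekly visit 2 (14 doses): 2.7 g/kg, 49%.
- Weekly visit 3 (21 doses): 4.1 g/kg, 75%.

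With the ±1 day windows accumulating, the ranges are 20–27%, 42–56% and 64–85%. Section 4.2.5 lists dosing among the weekly visit procedures. If that day's dose is given, the totals are 1.5, 2.9 and 4.3 g/kg (27%, 53% and 78%). With escalation on Day 3, the full course is 5.4 g/kg and the shares are 22%, 48% and 74%. A patient in state A who stops under section 8.1.2 receives one of these amounts; under the Treatment list, with enzymes still raised, the same patient goes on to the full course.

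**The case against.** The best defence is that the two operative body sections agree, and that the synopsis Treatment list is one departure from them. Study Design, with the slash read as *or*, matches the body. That limits the finding: a reader might infer three proven and mutually conflicting rules, but the text establishes two, plus one ambiguous statement. A reader might also infer that the rules clash in both mixed states. State B needs a particular reading of the slash or of liver function tests, so that is not established.

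Second, the link to entry is not wholly absent. Study Design ends treatment when hepatic dysfunction is reversed; I.4 defines that same term and uses the same bilirubin cut-off. This stands as a partial link, but the explanation in parentheses is generic and does not say which marker must recover.

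Third, nobody would stop a patient at baseline. This is right. Section 4.2.3 says "The Omegaven dose will be increased to 0.2 g/kg body weight (2 ml/kg" and section 4.1 says "All study patients will have a Screening Visit; Day 1, Day 2 and Day 3 visits; and weekly visits for one month". A reader might infer that enzyme-only patients are meant to receive no treatment; these passages rule that out. They do not say which criterion applies to such a patient at the weekly visits.

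Fourth, it might be inferred that home nurses would be making the stopping decision. The Protocol does not say so: section 4.3.1 gives laboratory review to the investigator or a qualified designee. Nor do the documents promise treatment until recovery, because every version allows treatment to end at 4 weeks with the injury unresolved.

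What remains is the conflict in state A and the limb that is met at entry.

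**Conclusion.** The point holds. Sections 4.2.5 and 8.1.2 contradict the synopsis Treatment list for any patient with bilirubin below 2 mg/dL and a raised enzyme, and neither reading of Study Design removes the contradiction. Read literally, the body's bilirubin limb cannot serve as a response criterion for an enzyme-only patient whose bilirubin was below 2 at entry. The Treatment limb likewise cannot serve for a bilirubin-only patient with normal enzymes.

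The consequence is moderate. Dose and the 4-week cap are the same under every version, and section 10.4 describes a single-arm study summarized descriptively. A reader might infer damage to an error rate or to the sample size, but the Protocol makes no claim that depends on either. The effect is on how long patients are treated and on the descriptive resolution outcome. The g/kg figures rest on the stated dosing assumptions and illustrate a single patient. How many of the roughly 30 planned patients would be affected cannot be derived from the document. This should be corrected.

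**What to change.** State one rule identically in the synopsis Study Design, the synopsis Treatment list, section 4.2.5 and section 8.1.2, tied to the abnormality that met I.4. For example:

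> Omegaven is given daily for up to 4 weeks or, if earlier, until each marker that met I.4 at baseline has resolved (bilirubin < 2 mg/dL; ALP, AST, ALT within normal range).

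Under this rule, none of the 46 qualifying patterns meets the stop at entry. At minimum, bilirubin below 2 must not stop treatment in a patient who qualified on an enzyme that is still raised. Merely aligning the Treatment list with the body and resolving the slash would remove the contradiction but leave that problem in place.

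Two clinical choices belong to the investigator: whether all or any of several qualifying markers must resolve, and what to do about a raised marker that did not itself qualify. A bilirubin-only patient with ALP at 2.9 times normal, for instance, would stop under the example wording once bilirubin is below 2, but continue under the present Treatment list. Whatever is chosen must read the same everywhere.

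The cost is a wording amendment in four places with IRB approval under section 11.2. No new tests are needed, because Table 2 and section 4.3.1 already provide a liver panel at every visit. The downside is that some patients are treated longer within the existing cap: at most about 5.5 − 1.3 = 4.2 g/kg more for one who would otherwise have stopped at the first weekly visit on schedule. The observed resolution rate may also be lower.

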8.1.3. Dispensation

Omegaven will be dispensed by the CTCA pharmacy and homecare pharmacies per the applicable policies and procedures for fat emulsions.

